3.3.6. Replacement of Patients

Patients prematurely withdrawn from the study will not be replaced. Patients may be rescreened at the Investigator's discretion.

4. INVESTIGATIONAL PRODUCT

4.1. Identity of the Investigational Product

Investigational product refers to both SPR720 and placebo in this Investigational Product section.

SPR720 will be administered po as 250 mg capsules containing SPR720 as the active substance with no additional excipients. The capsules are white, opaque, size 0, hard gelatin capsules containing a white powder. Placebo doses will also be administered po as white, opaque, size 0, hard gelatin capsules containing an approximately equivalent weight of microcrystalline cellulose (white powder).

SPR720 drug product and placebo are manufactured by Patheon UK Limited (Abingdon, Oxfordshire, UK) under Good Manufacturing Practice conditions and packaged, labeled, and distributed by Almac Clinical Services.

SPR720 and placebo are packaged in blister cards of 28 capsules each and then packaged into wallets that will be given to the patient.

Additional information is provided in the investigator's brochure (IB) and in the Pharmacy Manual.

Standard of care (SOC) will be obtained by the study sites or by prescription. Refer to the Product Package Inserts for detailed information regarding SOC treatments.

4.2. Dosage Schedule

Dosing for each treatment arm is displayed in [Table 1](#). Study drug will be taken po once daily for 28 days (Days 1 through 28). Dosing for Treatment Arms 1, 2, and 3 will take place at the clinic on study visit days. The clinic and patient should try to schedule clinic visits as early as possible in the morning to accommodate pre-dose study activities and dosing, preferably before a meal. Patients in Treatment Arms 1, 2, and 3 should make every effort to take the IP at the same time in the morning approximately an hour before a morning meal on an empty stomach. There are no liquid restrictions. Patients will receive a supply of IP and instructions for documenting at-home dosing. If a patient experiences IP tolerability issues while at home, the site should instruct the patient to call the Investigator. The Investigator may instruct the patient to take their dose with a snack or meal, if clinically indicated, to alleviate tolerability concerns. Dosing for Treatment Arm 4 (SOC) should occur per specific prescribing information instructions.

Table 1: Study Treatments

Treatment Arm 1	Double-blinded SPR720 IP 500 mg (2 capsules of 250 mg SPR720 and 2 capsules of placebo) po once daily
Treatment Arm 2	Double-blinded SPR720 IP 1000 mg (4 capsules of 250 mg SPR720) po once daily
Treatment Arm 3	Double-blinded placebo (4 capsules of placebo) po once daily
Treatment Arm 4	
Standard of Care regimen is at the Investigator's discretion; recommended 2-drug or 3-drug SOC, consisting of either:
 
 • Clarithromycin 500-1000 mg, plus ethambutol HCl 15 mg/kg po once daily or • Azithromycin 250-500 mg, plus ethambutol HCl 15 mg/kg po once daily 
Optional rifampin 600 mg or rifabutin 300 mg po once daily may be added to the SOC regimen for up to 28 days.
 
Inform the medical monitor of alternative SOC regimens and discuss concerns or questions.

Abbreviations: HCl=hydrochloride; IP=investigational product; po=orally; SOC=standard of care.

Note: Patients will be treated for 28 days.

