2. STUDY OBJECTIVES

2.1. Primary Objective

The primary objective of this study is to evaluate the PK of SPR719 generated from the orally (po) administered SPR720 prodrug in a patient population with NTM-PD.

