15. If female, is pregnant or breastfeeding
16. Has a corrected QT (QTc) interval on electrocardiogram (ECG) > 470 ms
17. Has consumed drugs or supplements that are strong cytochrome P450 (CYP)3A4 enzyme inducers or strong CYP3A4 inhibitors (see [Appendix 1](#)) within 4 weeks of randomization
18. Has consumed drugs or supplements that are substrates of the hepatic transporters OATP1B1 or OATP1B3 (see [Appendix 2](#)) within 1 week of randomization
19. Has a documented hypersensitivity reaction or anaphylaxis to SPR720 or any of the specified SOC medications
20. Has received any investigational medication in the year before the time of consent
21. Has any other condition or prior therapy, which, in the opinion of the Investigator, would make the patient unsuitable for this study, including compliance with all study assessments and adherence to the protocol schedule

Patients who are unable to comply with the requirements of the study or who in the opinion of the Investigator should not participate in the study are not eligible.

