4.7.2. Concomitant Treatments

Concomitant medications and treatments, defined as treatments taken after the first dose of IP and SOC, should be recorded in the eCRF according to completion guidelines. Medications and treatments taken before the first dose of IP or SOC will not be recorded in the eCRF.

Patients should not have used any systemic (po or IV) or inhaled antibiotic with activity versus MAC between screening and randomization. Drugs or supplements that are strong CYP3A4 enzyme inducers or inhibitors (see [Appendix 1](#)) within 4 weeks of randomization and during the study are prohibited. Hepatic transporters, OATP1B1 or OATP1B3, (see [Appendix 2](#)) within 1 week of randomization and during the study are prohibited.

Any medication or therapy that is taken by or administered to the patient during the study will be recorded (see completion guidelines for eCRF).

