8.1.4. Determination of Sample Size

This study will be conducted to evaluate the PK and safety of SPR720 in a patient population with NTM-PD and to evaluate the efficacy of SPR720 compared with placebo in patients with NTM-PD.

There is no formal statistical hypothesis planned, and the sample size is mainly based on an estimated number of patients needed to understand the PK and safety of patients in this study.

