APPENDIX 1. PROHIBITED INHIBITORS AND INDUCERS OF CYP3A

The following inhibitors and inducers of CYP3A are prohibited within 4 weeks before randomization and during the study:

CYP3A Strong Inhibitors	CYP3A Strong Inducers
Boceprevir	Carbamazepine
Cobicistat	Enzalutamide
Conivaptan	Mitotane
Danoprevir and ritonavir	Phenytoin
Elvitegravir and ritonavir	Rifampin
Grapefruit juice	St. John's wort
Indinavir and ritonavir	
Itraconazole	
Ketoconazole	
Lopinavir and ritonavir	
Paritaprevir and ritonavir and (ombitasvir and/or dasabuvir)	
Posaconazole	
Ritonavir	
Saquinavir and ritonavir	
Telaprevir	
Tipranavir and ritonavir	
Troleandomycin	
Voriconazole	
Clarithromycin	
Diltiazem	
Idelalisib	
Nefazodone	
Nelfinavir	

Abbreviation: CYP=cytochrome P450

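### The dosing text says liquids are unrestricted, but Appendix 1 prohibits grapefruit juice during the study, so a site or patient relying on the dosing text could allow a banned exposure (minor)

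*Combined protocol and SAP*

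**What the plan says.** Section 4.2 asks patients in Arms 1 to 3 to take the product in the morning, "approximately an hour before a morning meal on an empty stomach", and then adds: "There are no liquid restrictions". Footnote q to Table 2 (Section 5.1) repeats that sentence. Neither place makes an exception or refers to Appendix 1.

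Appendix 1 opens: "The following inhibitors and inducers of CYP3A are prohibited within 4 weeks before randomization and during the study". Its strong-inhibitor column includes "Grapefruit juice".

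Two parts of the body text send the reader to that appendix. Exclusion 17 (Section 3.3.2) applies to a patient who "Has consumed drugs or supplements that are strong cytochrome P450 (CYP)3A4 enzyme inducers or strong CYP3A4 inhibitors". Section 4.7.2 extends the rule past entry: listed items "within 4 weeks of randomization and during the study are prohibited". Both describe the listed items as medicines or supplements, and neither mentions food or drink.

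Section 2.1 states: "The primary objective of this study is to evaluate the PK of SPR719 generated from the orally (po) administered SPR720 prodrug". Section 8.1.1 gives the primary endpoints as Cmax, Tmax, AUC over the dosing interval and accumulation ratio, on Days 1 and 28.

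**The concern.** One drink is prohibited in an appendix and left unrestricted in the two places where a site looks for dosing instructions. The ban on the juice is explicit only as one line in the appendix list. The body text that leads there uses a description that a coordinator or patient might not apply to a breakfast drink.

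The subject of the conflict is drug exposure, which is what the trial is designed to describe. Noncompartmental analysis rests on the intensively sampled patients (Section 8.1.8), planned at 6 per arm in Section 3.1. Sparse-sampling concentrations from SPR720 recipients also feed the population PK model. An instruction that can let a listed inhibitor in is worth correcting in such a trial, even though nothing in the documents says how much it would matter.

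**Working it through.** No figure in the plan bears on this point. Section 8.1.4 says "There is no formal statistical hypothesis planned", so there is no power, effect size or variance to reproduce. The check is a comparison of texts.

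1. **Is grapefruit juice within the liquid sentence?** Yes. It is a liquid, and the sentence in Section 4.2 and footnote q has no qualifier.
2. **Is it within the ban?** Yes. Appendix 1 names it, and its heading sentence covers the four weeks before randomization and the study itself. Section 4.7.2 applies the appendix list during the study.
3. **Do the periods overlap?** Yes. Dosing runs from Day 1 to Day 28, all of it inside the banned period.
4. **Does either text yield to the other?** No. The dosing text does not mention prohibited substances, and Appendix 1 does not mention the dosing text.
5. **Would a reader of the body text be led to the ban?** Only by following exclusion 17 or Section 4.7.2 to the appendix. Their wording does not signal that a drink is on the list.
6. **How many doses are taken away from the clinic?** Clinic dosing is on visit Days 1, 7, 14, 21 and 28, which is 5 days. The planned number of home doses is 28 − 5 = 23 of 28. For these the patient's own instructions govern.
7. **Would intake be recorded?** Sections 4.6 and 5.1 name the date and time of each dose plus other requested information. Section 4.7.2 covers medications and therapies. No section names liquids, but the diary is not among the documents, so whether it asks about them is unknown.
8. **Can the PK effect be sized?** No. The documents give no CYP3A effect on SPR719 exposure and no reason for the ban.

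Steps 1 to 5 establish the conflict. Steps 6 and 7 show that staff observation or records cannot be assumed to catch every instance. Step 8 means that no size can be attached.

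**The case against.** The strongest reply is that the liquid sentence comes straight after the empty-stomach instruction and only clarifies it: no food, but fluids need not be withheld. On that reading it is not a licence for prohibited substances, which are dealt with in Section 4.7.2 and Appendix 1. A general sentence about dosing and a specific ban on one juice can both be obeyed.

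This reading is plausible, and it is one reason why the point is minor. It does not remove the conflict. The sentence does not say that it is limited in this way, and even as a fasting clarification it leaves the banned juice allowed at the moment of dosing.

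Three further replies stand in part:

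- **The ban can be found.** Exclusion 17 and Section 4.7.2 both point to Appendix 1. A reader might infer that any site following Section 4.2 would permit the juice. The documents support only that a site or patient relying on the dosing text could do so.
- **Key doses are supervised.** Day 1 and Day 28 doses are given in the clinic, so staff can see what accompanies them. The ban is not limited to what accompanies a dose, however, and the home doses lack that safeguard.
- **The diary may ask.** A reader might infer that juice intake could never be identified afterwards. That does not follow, because the diary collects further information that the protocol does not specify.

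A reader might also extend the point to caloric drinks and the empty-stomach instruction. That is a request for more detail, not a contradiction. Section 4.2 itself lets the Investigator allow a dose with a snack or meal for tolerability.

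**Conclusion.** The conflict is established by the text and is minor. Two places say without exception that liquids are unrestricted, one place prohibits a named liquid over the same period, and the linking text describes the list in terms that make the ban easy to miss. This conclusion needs no assumption beyond reading the sentences as written.

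The effect on PK cannot be quantified from the documents. A reader might still put a number on it. If one of 6 intensively sampled patients in an arm had exposure multiplied by f, the arithmetic mean would change by (5 + f)/6 and the geometric mean by f^(1/6). For an assumed f of 1.3 to 2 these give 1.05 to 1.167 and 1.045 to 1.122. The arithmetic is right, but neither the range for f nor the one-in-six frequency has a source in the documents, so it is not an estimate of bias. Nor is it established that juice on only Day 1 or only Day 28 would move that patient's accumulation ratio by the whole of f. That would require the full factor to act on the AUC of that single dosing interval.

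A reader might also infer that Appendix 1 exists to keep CYP3A inhibition out of the PK profiles. The protocol gives no reason for the list and does not say that SPR719 is a CYP3A substrate.

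**What to change.** Reconcile Section 4.2, Table 2 footnote q, exclusion 17, Section 4.7.2 and Appendix 1 so that all five give one consistent instruction on the listed juice. If the sponsor keeps the prohibition, a cross-reference to Appendix 1 in the two liquid sentences, and wording in exclusion 17 and Section 4.7.2 that covers every item listed there, would be enough. If the sponsor does not keep it, the appendix entry has to be brought into line. Which rule applies is the sponsor's decision. Carry the result into the patient dosing instructions.

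The cost is a few words in each affected place and a matching line in the patient material. No procedures, visits or patients are added, and no planned analysis changes.

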- o. Patient-collected pooled expectorated sputum collected on Days -1 , 6, 13, 20, and 27 (i.e., on the day before clinical study visits over an approximate 24-h period). The patients will bring the pooled samples to the clinic for processing and shipment to the central laboratory.
- p. Respiratory samples using a standard protocol for collecting induced sputum will be used at all sites. Induction will be performed in the clinic with hypertonic saline administered by nebulizer. Induced sputum samples will be collected at screening, and for Treatment Arms 1, 2, and 3 on Day 56 (Follow-up). On Days 1, 7, 14, 21, and 28 sputum samples will be collected pre-dose. Induced sputum samples will be shipped to the central laboratory.
- q. Patients randomized to Treatment Arms 1, 2, and 3 will be double blinded, and Treatment Arm 4 (SOC) will be open label. Dosing for patients in Treatment Arms 1, 2, and 3 will take place at the clinic on study visit days. The clinic and patient should try to schedule clinic visits in the morning as early as possible to accommodate pre-dose study activities and dosing, preferably before a meal. Patients randomized to Treatment Arms 1, 2, and 3 should make every effort to take the IP at the same time in the morning approximately 1 h (no less than 30 min) before a morning meal on an empty stomach. There are no liquid restrictions. Patients will receive a supply of IP and instructions for documenting at-home dosing, which will include the date and time of each IP or SOC dose taken, along with other requested information related to IP administration. Dosing for Treatment Arm 4 (SOC) should occur per specific prescribing information instructions.

█ [REDACTED]

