8.1. Endpoints

8.1.1. Primary

- Maximum plasma concentration (C_{max}), time to reach C_{max} (T_{max}), area under the concentration-time curve from zero to τ , where τ is the dosing interval ($AUC_{0-\tau}$), and accumulation ratio of SPR719 on Day 1 and Day 28

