8.1.8. Pharmacokinetic Analyses

Dates and times of blood samples as well as dates and times of study drug administration will be recorded. Plasma concentration-time data from intensive PK sampling patients will be subjected to noncompartmental PK analysis. Day 1 and Day 28 PK parameters including, but not limited to, C_{max} , T_{max} , area under the concentration-time curve from zero to last concentration (AUC_{last}), $AUC_{0-\tau}$, accumulation ratio, and plasma concentration at the end of a dosing interval at steady state (taken directly before next administration) (C_{trough}) will be determined when appropriate for SPR719. Concentration data from sparse sampling will be compiled for summary statistics of C_{trough} across various days. Concentration data from SPR720 recipients will be used for the development of a PK Population model, for PK analysis, and for estimation of individual PK profiles in patients with sparse sampling, which will be reported in a separate report.

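### Section 4.2 lets food state change between Day 1 and Day 28, yet food state is neither a named PK data item nor used in the analysis of the accumulation ratio

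*Combined protocol and SAP*

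**What the plan says.** Section 4.2 asks patients in Arms 1 to 3 to make every effort to "take the IP at the same time in the morning approximately an hour before a morning meal on an empty stomach". Footnote q to the Schedule of Assessments (Section 5.1, Table 2) gives the same instruction with a minimum gap: "approximately 1 h (no less than 30 min) before a morning meal on an empty stomach".

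Section 4.2 then goes further than the footnote. It opens with home dosing: "If a patient experiences IP tolerability issues while at home, the site should instruct the patient to call the Investigator". The next sentence reads: "The Investigator may instruct the patient to take their dose with a snack or meal, if clinically indicated, to alleviate tolerability concerns". No end date is set and the profile days are not mentioned. Footnote q does not carry this permission.

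The doses on PK days are supervised: "Dosing for Treatment Arms 1, 2, and 3 will take place at the clinic on study visit days". For those visits, dosing before a meal is stated as a preference.

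The primary endpoint (Section 8.1.1) is SPR719 Cmax, Tmax, AUC over the dosing interval and "accumulation ratio of SPR719 on Day 1 and Day 28". Section 8.1.8 derives these by noncompartmental analysis in the intensive-PK patients. On dosing data it says: "Dates and times of blood samples as well as dates and times of study drug administration will be recorded". Food state appears neither there nor in the PK Population definition (Section 8.1.5).

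**The concern.** The accumulation ratio is a within-patient comparison of Day 28 with Day 1. It measures accumulation only if nothing else that affects exposure changed in between. The permission is triggered by a tolerability problem at home, so it takes effect after the Day 1 clinic dose, in one direction: fasted to fed.

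If food alters SPR719 exposure, a switcher's ratio carries both effects, and one ratio cannot separate them. An investigator-approved fed dose is within the protocol, so it need not appear in the deviation listing (Section 8.1.6). The intensive-PK groups are small, so one or two such patients can matter. Food state that is not recorded at the time cannot reliably be recovered after database lock.

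**Working it through.** **Inputs from the protocol.** Sections 3.1 and 4.3 give at least 18 intensive-PK patients randomized 1:1:1, so 18/3 = 6 per arm, or 12 on SPR720. With 72 at the sparse sites the total is 72 + 18 = 90, as stated. Section 8.1.4 plans no formal hypothesis, so there is no power figure to reproduce.

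**Assumed inputs, because the documents give none.**
- F, the fed/fasted AUC ratio: 0.6 to 1.7.
- R, the true AUC accumulation ratio: 1.5 where a value is needed.
- Linear kinetics with superposition, and a fasted Day 1 dose.

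Take the Day 1 AUC as 1. The Day 28 AUC is then the contribution of the Day 28 dose (1) plus carry-over from earlier doses (R - 1).

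**Case A: the Day 28 dose and the doses before it are fed.** Observed ratio = F x R, so the patient's ratio is off by the factor F.

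**Case B: the preceding home doses are fed and the Day 28 clinic dose is fasted.** Observed ratio = 1 + (R - 1) x F. The patient's error factor is [1 + (R - 1)F]/R:
- F = 0.6: (1 + 0.5 x 0.6)/1.5 = 1.30/1.5 = 0.867
- F = 1.7: (1 + 0.5 x 1.7)/1.5 = 1.85/1.5 = 1.233

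**Effect on the arm.** With k switchers among 6, the geometric mean ratio is multiplied by (error factor)^(k/6).

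| Case | F | Patient's factor | 1 of 6 | 2 of 6 |
|---|---|---|---|---|
| A | 0.6 | 0.600 | 0.918 (-8%) | 0.843 (-16%) |
| A | 1.7 | 1.700 | 1.092 (+9%) | 1.193 (+19%) |
| B, R = 1.5 | 0.6 | 0.867 | 0.976 (-2.4%) | 0.953 (-4.7%) |
| B, R = 1.5 | 1.7 | 1.233 | 1.036 (+3.6%) | 1.072 (+7.2%) |

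Both cases give no bias if F = 1. Case B also gives none if R = 1, because nothing carries over.

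The geometric mean is my choice of scale. Section 8 names means and medians in general and does not name it. For an arithmetic mean with equal true ratios, one switcher in case A gives (5 + 0.6)/6 = 0.933 to (5 + 1.7)/6 = 1.117, which is the same order of size.

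**How likely is a switcher?** The chance of at least one among n patients is 1 - (1 - p)^n. The switch rate p is assumed:

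| p | n = 6 | n = 12 |
|---|---|---|
| 5% | 27% | 46% |
| 10% | 47% | 72% |
| 20% | 74% | 93% |

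**The case against.** The strongest reply is that the natural reading keeps the profile doses fasted. The permission follows a sentence about problems at home. Day 28 is dosed in clinic, early in the morning. The every-effort fasting instruction is not limited to home doses, and footnote q attaches it to the whole dosing row, Days 1 and 28 included. This has force: on that reading case B applies, and the distortion is much smaller. It does not settle the matter, because Section 4.2 makes no exception for profile days, and case B is not zero when the drug accumulates and food matters.

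A second reply is that a switch would leave a trace. The diary takes other dosing information besides date and time (Section 4.6, footnote q). A tolerability problem after the first dose is an AE (Section 6.3), the AE page has an action-taken item (Section 6), and measures applied go into the eCRF as applicable (Section 6.4). A reader might infer that switches would pass wholly unnoticed; these provisions make that too strong. None of them commits to food state, however, and the diary covers home doses whereas the profile doses are given in clinic.

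A third reply is that a detailed SAP is due before database lock (Section 8), that Section 8.1.8 determines parameters when appropriate, and that the analysis is descriptive with individual data listed. All true. A later SAP can still use only what was collected.

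Two further readings are tempting and should be resisted:
- **Every switcher's ratio equals accumulation times the food effect.** This holds only in case A.
- **Switching will be commoner at 1000 mg and will distort the dose comparison.** The documents give no tolerability difference between the doses. Section 1.2 says only that SPR720 was well tolerated in healthy volunteers for up to 14 days.

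**Conclusion.** The gap is real and modest. As written, the plan allows a change in food state between the two profile days, does not name food state as PK data and does not use it in the analysis. In a patient who switches, the Day 28 parameters and the accumulation ratio can therefore mix accumulation with a food effect.

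One switcher in six moves the arm's ratio by -8% to +9% if the Day 28 dose is fed along with those before it, and by about -2.4% to +3.6% if only the preceding home doses are. These figures rest on assumed F of 0.6 to 1.7, R of 1.5 in the second case, and linear kinetics. The true size is unknown and may be zero. Day 1 parameters are unaffected by a later switch. The point does not undermine the primary endpoint as a whole; it is worth acting on because the remedy is cheap and has to be in place while data are collected.

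**What to change.** 1. **Data.** Record on the eCRF the food state of every dose tied to a PK sample and of the home doses before it, with the date of any switch. The preceding doses are needed because of case B.
2. **Analysis, Section 8.1.8.** Keep the accumulation ratio in all evaluable patients. Flag patients whose food state changed between Day 1 and Day 28 or in the doses before Day 28. Add a summary restricted to patients with unchanged food state, noting that it drops those who switched for intolerance and is therefore a selected group. Test food state as a covariate in the population PK model.
3. **Text.** Reconcile Section 4.2 with Table 2 footnote q, and state whether the snack-or-meal permission applies on profile days. Which way this is resolved is for the sponsor and investigators; no dosing rule is proposed here.

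Cost: a small addition to the eCRF, a few sentences in Section 8.1.8 and one clarification. The restricted summary will have a smaller n.
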